## 9.9 Sample Size and Power Calculations

# 9.9.1 Sample Size and Power for Efficacy Analyses

# 9.9.1.1 Sample Size and Power for Testing the Primary Efficacy Hypothesis

The sample size of approximately 3300 was selected to ensure collection of adequate safety information on the use of MK-1654 in this otherwise healthy population of pre-term and full-term infants. This study will randomize approximately 2200 healthy infants into the MK-1654 group and approximately 1100 healthy infants into the placebo group. A total of approximately 167 cases of RSV-associated MALRI in the MK-1654 and placebo groups are expected to accrue by the end of the study, under the following assumptions: 1) incidence of RSV-associated MALRI in the placebo group is 10% per season; 2) efficacy=70%, so that the incidence of RSV-associated MALRI in the MK-1654 group is 3% per season; and 3) attrition rate is 5%. Under these assumptions, there is >95% power to demonstrate that the efficacy of MK-1654 compared to placebo to prevent RSV-associated MALRI is >25% if the underlying efficacy is 70% at an overall 1-sided Type 1 error of 2.5%. The calculations are based on a simulation study for the modified Poisson regression and carried out using the SAS software.

#### 9.9.1.2 Sample Size and Power for Testing the Secondary Efficacy Hypothesis

RSV-associated hospitalization is the secondary efficacy endpoint. A total of approximately 33 cases of RSV-associated hospitalization in the MK-1654 and placebo groups are expected to accrue by the end of the study, under the following assumptions: 1) incidence of RSV-associated hospitalization in the placebo group is 2% per season; 2) efficacy=70%, so that the incidence of RSV-associated hospitalization in the MK-1654 group is 0.6% per season; and 3) attrition rate is 5%. Under these assumptions, there is 93.6% power to demonstrate that the efficacy of MK-1654 compared to placebo to prevent RSV-associated hospitalization is >0%

if the underlying efficacy is 70% at an overall 1-sided Type 1 error of 2.5%. The calculations are based on a simulation study for the modified Poisson regression and carried out using the SAS software.

# 9.9.2 Sample Size and Power for Safety Analyses

The probability of observing at least 1 SAE in this study depends on the number of participants treated and the underlying percentage of participants with a SAE in the study population. Calculations below assume that 100% of the randomized participants will be evaluable for safety analyses. If the underlying incidence of an SAE is 0.069% (1 of every 1456 participants receiving the MK-1654), there is an 80% chance of observing at least 1 SAE among 2200 participants in the MK-1654 group. If the underlying incidence of an SAE is 0.033% (1 of every 3039 participants receiving the MK-1654), there is a 50% chance of observing at least 1 SAE among 2200 participants in the MK-1654 group. If no SAEs are observed among the 2200 participants in the MK-1654 group, this study will provide 97.5% confidence that the underlying percentage of participants with an SAE is <0.139% (1 in every 720 participants) in the MK-1654 group.

The percentage point differences between the 2 groups that could be detected with 80% probability for a variety of hypothetical underlying incidences of an AE are summarized in Table 9. These calculations assume 2200 participants in the MK-1654 group and 1100 participants in the placebo group and are based on a 2-sided 5% alpha level. The calculations are based on an asymptotic method proposed by Farrington and Manning (1990) [Farrington, C. P. 1990]; no multiplicity adjustments were made.

Table 9 Differences in Incidence of Adverse Event Rates Between the 2 Groups That can be Detected With an ~80% Probability (Assuming 2-sided 5% Alpha Level With 2200 Participants in the MK-1654 Group and 1100 Participants in the Placebo Group)

Incidence of	Incidence of Adverse Event		
Placebo (%)	MK-1654 (%)	Percentage Points	
0.1	0.8	0.7	
2.0	3.8	1.8	
5.0	7.5	2.5	
10.0	13.3	3.3	
15.0	18.9	3.9	
20.0	24.3	4.3	
30.0	34.9	4.9	

Incidences presented here are hypothetical and do not represent actual adverse experiences in either group. Based on an asymptotic method [Farrington, C. P. 1990].

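### The safety-precision figures in Section 9.9.2 do not follow from 2200 infants: zero events excludes 0.168% (1 in 597) with 97.5% confidence, not 0.139% (1 in 720)

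*Combined protocol and SAP*

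**What the plan says.** Section 9.9.2 (Sample Size and Power for Safety Analyses) makes three statements about the MK-1654 group, all for 2200 participants:

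- **80% chance of at least one SAE:** "If the underlying incidence of an SAE is 0.069% (1 of every 1456 participants receiving the MK-1654), there is an 80% chance".
- **50% chance of at least one SAE:** "If the underlying incidence of an SAE is 0.033% (1 of every 3039 participants receiving the MK-1654), there is a 50% chance".
- **Zero events:** "If no SAEs are observed among the 2200 participants in the MK-1654 group", then "this study will provide 97.5% confidence that the underlying percentage of participants with an SAE is <0.139% (1 in every 720 participants" in that group.

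The section leaves no room for an attrition adjustment: "Calculations below assume that 100% of the randomized participants will be evaluable for safety analyses". The group size agrees with Section 9.9.1.1: "This study will randomize approximately 2200 healthy infants into the MK-1654 group and approximately 1100 healthy infants into the placebo group". No method is named for the three figures. The method reference in the section belongs to Table 9, which concerns differences between groups.

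Section 9.9.1.1 also says that the total of about 3300 "was selected to ensure collection of adequate safety information on the use of MK-1654". Section 4.1 gives the same reason, and justifies the optional extra 10% of participants on safety grounds too.

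**The concern.** All three statements come from one elementary relation between an event rate, a sample size and the probability of seeing at least one event. With the sample size fixed at 2200 and everyone evaluable, each has a single answer, and none of the printed rates matches it.

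The zero-event bound matters most. A reader would use it to say which rates of a specific rare event the trial can exclude if none occurs. As printed, it claims to exclude rates between 0.139% and 0.168% at a confidence the data would not support. Section 9.6.2 designates no Tier 1 safety events, so no safety endpoint is formally tested and descriptive statements of precision carry more of the weight. A wrong figure here could also be carried into a study report or a benefit-risk discussion.

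**Working it through.** **Inputs (Section 9.9.2):** n = 2200; 100% evaluable; zero events for the bound; 97.5% confidence; stated rates 1 in 1456, 1 in 3039 and 1 in 720.

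**Formulas:**
- Probability of at least one event at rate p: 1 − (1 − p)^n.
- Rate giving probability c of at least one event: p = 1 − (1 − c)^(1/n). With zero events observed, this is also the exact (Clopper-Pearson) upper bound at one-sided confidence c.

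**Step 1. Is each printed pair consistent with itself?** 1/1456 = 0.0687%, 1/3039 = 0.0329% and 1/720 = 0.1389%. Each percentage agrees with its own denominator, so a misread digit is not the explanation.

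**Step 2. What do the stated rates deliver with 2200 infants?**
- 1 − (1 − 1/1456)^2200 = 77.9% (stated 80%)
- 1 − (1 − 1/3039)^2200 = 51.5% (stated 50%)
- 1 − (1 − 1/720)^2200 = 95.3% (stated 97.5%)

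**Step 3. Which rates match the stated probabilities?**

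| Statement | Plan | Formula | Result for n = 2200 |
|---|---|---|---|
| 80% chance of at least 1 | 0.069% (1 in 1456) | 1 − 0.2^(1/2200) | 0.0731% (1 in 1367) |
| 50% chance of at least 1 | 0.033% (1 in 3039) | 1 − 0.5^(1/2200) | 0.0315% (1 in 3174) |
| 97.5% bound, zero events | 0.139% (1 in 720) | 1 − 0.025^(1/2200) | 0.1675% (1 in 597) |

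A Poisson calculation gives almost the same bound (1 in 596). The ratio of the correct bound to the stated one is 0.1675/0.139 = 1.21.

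**Step 4. Does another sample size explain all three?** Solving n = ln(1 − c)/ln(1 − p) for each stated rate gives about 2343 (80%), 2106 (50%) and 2654 (97.5%). No single n fits.

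**Step 5. Does another method or assumption give 0.139% at 97.5%?**
- *Full 10% over-enrolment:* 3630 infants at 2:1 gives 2420 on MK-1654. The bound is 0.152% (about 1 in 657), and 1 in 720 carries 96.5% confidence.
- *5% attrition, as in the efficacy calculation:* n = 2090 gives 0.176%, further away, and conflicts with the 100% evaluable assumption.
- *Wilson at 97.5%:* 0.174%. *Jeffreys at 97.5%:* 0.114%.
- *One-sided 95% exact, or 97.5% mid-P:* both 0.136% (1 in 735). *Rule of three:* 3/2200 = 0.136% (1 in 733).

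The last group comes closest, so the printed figure behaves like a 95% bound labelled 97.5%. A one-sided 95% bound with n = 2156 (98% of 2200) would give 1 in 720. That needs two departures from the text, and the same n gives 1 in 1340 and 1 in 3111 for the other two statements. The cause remains a guess, and the error does not depend on it.

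**Step 6. Table 9.** Power for 1100 versus 2200 infants at the seven tabulated pairs runs from 77% to 82%, consistent with its label of about 80%. The table is not affected.

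**The case against.** The best case on the other side concerns weight, since the arithmetic of the bound is not in dispute.

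- **Two of the three misses are small.** 77.9% against 80% and 51.5% against 50% would not change a reader's view, and the 50% statement is on the cautious side. This stands: those two corrections are tidying, and the zero-event bound is the substantive one.
- **No decision rests on the paragraph.** It feeds no test, alpha, stopping rule or analysis population. The 4.7% chance left outside the stated bound is a shortfall in confidence, not Type 1 error inflation. This stands too.
- **Zero SAEs of any kind is an unlikely outcome.** The SAE definition in Section 10.3.3 includes inpatient hospitalization, and SAEs are collected for at least 365 days. The bound is useful mainly for a specific rare event. That narrows its use, but a specific rare event is where such a bound would be quoted.
- **The sample size was not shown to depend on 1 in 720.** Section 9.9.1.1 cites safety information in general, sets no target rate and does not point to this bound. That is fair: nothing suggests 1 in 597 would have led to a different trial. Even so, Section 9.9.2 is where the plan puts numbers on the safety information that the size is meant to secure.

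None of this makes the printed bound correct.

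**Conclusion.** The concern holds. The 97.5% zero-event bound is understated by about 17%, and the confidence attached to 1 in 720 is overstated by 2.2 percentage points. Two of the three figures, including this one, make the design look more informative than it is.

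The conclusion rests only on the section's own inputs and on independent participants with a common event probability. Exact binomial and Poisson calculations agree. Confirmatory inference and the sample size are untouched, so this is a correction to stated safety precision and not a design fault.

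**What to change.** In Section 9.9.2, keep n = 2200, 100% evaluable and the stated probabilities, and replace the three rates:

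- 80% chance of at least one SAE: 0.073% (1 in 1367)
- 50% chance of at least one SAE: 0.032% (1 in 3174)
- Zero SAEs, 97.5% confidence: below 0.168% (1 in 597)

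Name the method (exact binomial, one-sided) so that a reader can check the figures. If the sponsor would rather quote a one-sided 95% bound, the figure is 0.136% (1 in 735) and the confidence level must be changed to match.

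The cost is three numbers and a short method note in one paragraph. The stated precision becomes slightly less favourable, and nothing else in the plan needs to change.

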#### 9.10 Subgroup Analyses

The consistency of the treatment effect will be assessed descriptively by category for the classification variables listed below. Efficacy of MK-1654 against RSV-associated MALRI will be estimated separately in (1) Southern Hemisphere and Northern Hemisphere regions; (2) the early and moderate pre-term infants ( $\geq$ 29 to <35 weeks gestational age) and late pre-term and full-term infants ( $\geq$ 35 weeks gestational age) subgroups; (3) age groups at the time of consent (<6 months;  $\geq$ 6 months); (4) weight groups at the time of consent. In addition to the 2 age groups, efficacy will also be summarized in infants  $\leq$ 2 weeks of age. The incidence of RSV-associated MALRI in each treatment group, the estimate of efficacy, and the nominal 95% CI will be reported for each subgroup.

Subgroup analyses of safety and PK profiles will be summarized descriptively by age groups at randomization. The descriptive statistics will be reported for each subgroup.

# 9.11 Compliance (Medication Adherence)

Given that participants will receive just a single dose of MK-1654 or a single dose of placebo, compliance will not be calculated. However, the number and proportion of randomized participants receiving each treatment will be summarized (see Section 9.12).

### 9.12 Extent of Exposure

The extent of exposure will be summarized by the number and proportion of randomized participants administered MK-1654 and the number and proportion of randomized participants administered placebo.

# 10 SUPPORTING DOCUMENTATION AND OPERATIONAL CONSIDERATIONS

#### 10.1 Appendix 1: Regulatory, Ethical, and Study Oversight Considerations

#### 10.1.1 Code of Conduct for Clinical Trials

Merck Sharp & Dohme LLC, Rahway, NJ, USA (MSD)

#### **Code of Conduct for Interventional Clinical Trials**

#### I. Introduction

#### A. Purpose

MSD, through its subsidiaries, conducts clinical trials worldwide to evaluate the safety and effectiveness of our products. As such, we are committed to designing, implementing, conducting, analyzing, and reporting these trials in compliance with the highest ethical and scientific standards. Protection of participants in clinical trials is the overriding concern in the design and conduct of clinical trials. In all cases, MSD clinical trials will be conducted in compliance with local and/or national regulations (including all applicable data protection regulations), and International Council for Harmonisation Good Clinical Practice (ICH-GCP), and also in accordance with the ethical principles that have their origin in the Declaration of Helsinki.

#### B. Scope

Highest ethical and scientific standards shall be endorsed for all clinical interventional investigations sponsored by MSD irrespective of the party (parties) employed for their execution (e.g., contract research organizations, collaborative research efforts). This Code is not intended to apply to trials that are observational in nature, or which are retrospective. Further, this Code does not apply to investigator-initiated trials, which are not under the full control of MSD.

## II. Scientific Issues

#### A. Trial Conduct

#### 1. Trial Design

Except for pilot or estimation trials, clinical trial protocols will be hypothesis-driven to assess safety, efficacy and/or pharmacokinetic or pharmacodynamic indices of MSD or comparator products. Alternatively, MSD may conduct outcomes research trials, trials to assess or validate various endpoint measures, or trials to determine patient preferences, etc.

The design (i.e., participant population, duration, statistical power) must be adequate to address the specific purpose of the trial. Participants must meet protocol entry criteria to be enrolled in the trial.

#### 2. Site Selection

MSD selects investigative sites based on medical expertise, access to appropriate participants, adequacy of facilities and staff, previous performance in clinical trials, as well as budgetary considerations. Prior to trial initiation, sites are evaluated by MSD personnel (or individuals acting on behalf of MSD) to assess the ability to successfully conduct the trial.

#### 3. Site Monitoring/Scientific Integrity

Investigative trial sites are monitored to assess compliance with the trial protocol and Good Clinical Practice (GCP). MSD reviews clinical data for accuracy, completeness, and consistency. Data are verified versus source documentation according to standard operating procedures. Per MSD policies and procedures, if fraud,

PROTOCOL/AMENDMENT NO.: 004-05

scientific/research misconduct or serious GCP-non-compliance is suspected, the issues are investigated. When necessary, the clinical site will be closed, the responsible regulatory authorities and ethics review committees notified.

#### **B.** Publication and Authorship

Regardless of trial outcome, MSD commits to publish the primary and secondary results of its registered trials of marketed products in which treatment is assigned, according to the pre-specified plans for data analysis. To the extent scientifically appropriate, MSD seeks to publish the results of other analyses it conducts that are important to patients, physicians, and payers. Some early phase or pilot trials are intended to be hypothesis-generating rather than hypothesis testing; in such cases, publication of results may not be appropriate since the trial may be underpowered and the analyses complicated by statistical issues such as multiplicity.

MSD's policy on authorship is consistent with the recommendations published by the International Committee of Medical Journal Editors (ICMJE). In summary, authorship should reflect significant contribution to the design and conduct of the trial, performance or interpretation of the analysis, and/or writing of the manuscript. All named authors must be able to defend the trial results and conclusions. MSD funding of a trial will be acknowledged in publications.

#### III. Participant Protection

# A. Regulatory Authority and Ethics Committee Review (Institutional Review Board [IRB]/Independent Ethics Committee [IEC])

All protocols and protocol amendments will be submitted by MSD for regulatory authority acceptance/authorization prior to implementation of the trial or amendment, in compliance with local and/or national regulations.

The protocol, protocol amendment(s), informed consent form, investigator's brochure, and other relevant trial documents must be reviewed and approved by an IRB/IEC before being implemented at each site, in compliance with local and/or national regulations. Changes to the protocol that are required urgently to eliminate an immediate hazard and to protect participant safety may be enacted in anticipation of ethics committee approval. MSD will inform regulatory authorities of such new measures to protect participant safety, in compliance with local and/or national regulations.

#### B. Safety

The guiding principle in decision-making in clinical trials is that participant welfare is of primary importance. Potential participants will be informed of the risks and benefits of, as well as alternatives to, trial participation. At a minimum, trial designs will take into account the local standard of care.

All participation in MSD clinical trials is voluntary. Participants enter the trial only after informed consent is obtained. Participants may withdraw from an MSD trial at any time, without any influence on their access to, or receipt of, medical care that may otherwise be available to them.

#### C. Confidentiality

MSD is committed to safeguarding participant confidentiality, to the greatest extent possible. Unless required by law, only the investigator, Sponsor (or individuals acting on behalf of MSD), ethics committee, and/or regulatory authorities will have access to confidential medical records that might identify the participant by name.

#### D. Genomic Research

Genomic research will only be conducted in accordance with a protocol and informed consent authorized by an ethics committee.

PROTOCOL/AMENDMENT NO.: 004-05

#### IV. Financial Considerations

#### A. Payments to Investigators

Clinical trials are time- and labor-intensive. It is MSD's policy to compensate investigators (or the sponsoring institution) in a fair manner for the work performed in support of MSD trials. MSD does not pay incentives to enroll participants in its trials. However, when enrollment is particularly challenging, additional payments may be made to compensate for the time spent in extra recruiting efforts.

MSD does not pay for participant referrals. However, MSD may compensate referring physicians for time spent on chart review and medical evaluation to identify potentially eligible participants.

#### B. Clinical Research Funding

Informed consent forms will disclose that the trial is sponsored by MSD, and that the investigator or sponsoring institution is being paid or provided a grant for performing the trial. However, the local ethics committee may wish to alter the wording of the disclosure statement to be consistent with financial practices at that institution. As noted above, all publications resulting from MSD trials will indicate MSD as a source of funding.

#### C. Funding for Travel and Other Requests

Funding of travel by investigators and support staff (e.g., to scientific meetings, investigator meetings, etc.) will be consistent with local guidelines and practices.

#### V. Investigator Commitment

Investigators will be expected to review MSD's Code of Conduct as an appendix to the trial protocol, and in signing the protocol, agree to support these ethical and scientific standards.

#### 10.1.2 Financial Disclosure

Financial Disclosure requirements are outlined in the US Food and Drug Administration Regulations, Financial Disclosure by Clinical Investigators (21 CFR Part 54). It is the Sponsor's responsibility to determine, based on these regulations, whether a request for Financial Disclosure information is required. It is the investigator's/subinvestigator's responsibility to comply with any such request.

The investigator/subinvestigator(s) agree, if requested by the Sponsor in accordance with 21 CFR Part 54, to provide his/her financial interests in and/or arrangements with the Sponsor to allow for the submission of complete and accurate certification and disclosure statements. The investigator/subinvestigator(s) further agree to provide this information on a Certification/Disclosure Form, commonly known as a financial disclosure form, provided by the Sponsor. The investigator/subinvestigator(s) also consent to the transmission of this information to the Sponsor in the United States for these purposes. This may involve the transmission of information to countries that do not have laws protecting personal data.

#### 10.1.3 Data Protection

The Sponsor will conduct this study in compliance with all applicable data protection regulations.

Participants will be assigned a unique identifier by the Sponsor. Any participant records or datasets that are transferred to the Sponsor will contain the identifier only; participant names or any information that would make the participant identifiable will not be transferred.

The participant must be informed that his/her personal study-related data will be used by the Sponsor in accordance with local data protection law. The level of disclosure must also be explained to the participant.

The participant must be informed that his/her medical records may be examined by Clinical Quality Assurance auditors or other authorized personnel appointed by the Sponsor, by appropriate IRB/IEC members, and by inspectors from regulatory authorities.

## 10.1.3.1 Confidentiality of Data

By signing this protocol, the investigator affirms to the Sponsor that information furnished to the investigator by the Sponsor will be maintained in confidence, and such information will be divulged to the IRB, IEC, or similar or expert committee; affiliated institution and employees, only under an appropriate understanding of confidentiality with such board or committee, affiliated institution and employees. Data generated by this study will be considered confidential by the investigator, except to the extent that it is included in a publication as provided in the Publications section of this protocol.

